### 8.2 Study procedures

#### 8.2.1 QA

Participating centres will have different scanning platforms, with different vendors and different generation of scanners providing more or less advanced sequences. Therefore the sequences for this study need to be optimized for each scanning platform to exploit its full potential. To ensure consistent quantification between the participating centres, a quality assurance procedure will be followed prior to inclusion of the first patient. This procedure consists of imaging of calibration phantoms with the proposed sequences for the study. The quantitative values will be compared to the ground truth phantom values. In addition, a set of benchmark sequences will be scanned. These consist of robust techniques that are available on each platform, but that typically are too slow for clinical use. Comparison of the obtained

values with the proposed study sequences and ground truth values will be done to assess the origin of potential differences in values so as to facilitate optimization of the study sequences. The results will be sent to the trial coordinators for analysis. Upon approval of the sequences specific for the centre by the trial coordinators, inclusion in the study in a participating centre can start.

### **8.2.2 Patient recruitment**

Patients who are eligible for inclusion in the study are informed by their physician about the study. After respite according to national guidelines, the patients will be contacted to ask whether they are willing to participate. The patients are then asked to sign informed consent.

### **8.2.3 MRI exam**

Each patient will undergo MRI before initiation of external beam radiotherapy. The MRI should be within 4 weeks before first EBRT fraction.

The MRI exam will consist of the following sequences, all axially sliced:

- Quantitative T2 mapping
- B0 mapping
- Diffusion-weighted MRI
- B1 mapping (for patients scanned on 3T MRI platforms)
- Quantitative T1 mapping
- DCE-MRI

MRI at time of first brachytherapy fraction is optional and will consist of the following sequences:

- Quantitative T2 mapping (axially sliced)
- B0 mapping
- Diffusion-weighted MRI

### **8.2.4 Recording and reporting**

Reporting of clinical status at diagnosis, and treatment parameters are to EMBRACE CRFs

### **8.2.5 Follow-up investigations**

Follow-up is according to EMBRACE II follow-up schedule.

### **8.3 Withdrawal of individual subjects**

Subjects can leave the study at any time for any reason if they wish to do so without any consequences. The investigator can decide to withdraw a subject from the study for urgent medical reasons.

### **8.4 Replacement of individual subjects after withdrawal**

If a participant withdraws from the study, an extra patient will be included.

### **8.5 Follow-up of subjects withdrawn from treatment**

Patients who have withdrawn from the imaging study will continue their enrolment into EMBRACE II

### **8.6 Premature termination of the study**

No measures need to be taken if the study is terminated prematurely.

## SAFETY REPORTING

### 8.7 Adverse and Serious Adverse Events

Adverse events are defined as any undesirable experience occurring to a subject during the Study which are related to administration of contrast and imaging. All adverse events reported spontaneously by the subject or observed by the investigator or his staff will be recorded.

A serious adverse event is any untoward medical occurrence or effect that at any dose

- results in death;
- is life threatening (at the time of the event);
- requires hospitalisation or prolongation of existing inpatients' hospitalisation;
- results in persistent or significant disability or incapacity;
- is a congenital anomaly or birth defect;
- is a new event of the trial likely to affect the safety of the subjects, such as an unexpected outcome of an adverse reaction, lack of efficacy of an IMP used for the treatment of a life threatening disease, major safety finding from a newly completed animal study, etc. All SAEs will be reported to the accredited MREC that approved the protocol, according to the requirements of that MREC.

#### 8.7.1 Suspected unexpected serious adverse reactions (SUSARs)

Not applicable

#### 8.7.2 Annual safety report

Not applicable

### 8.8 Follow-up of adverse events

All adverse events will be followed until they have abated, or until a stable situation has been reached. Depending on the event, follow - up may require additional tests or medical procedures as indicated, and/or referral to the general physician or a medical specialist.

## 9. IMAGE ANALYSIS

The MRI exam will result in a T1 and a T2 scan, DWI-MRI, and DCE-MRI.

Imaging data will be uploaded on a secure server, and centralised data analysis will be performed at Aarhus University Hospital (AUH) and Netherlands Cancer Institute (NKI).

### **Tumour volume delineation**

Delineation of GTV on T2 weighted images will be performed by the institution treating the patient.

### **DCE-MRI**

The image analysis of the dynamic contrast enhanced scans will be done at Aarhus University Hospital by using a number of in-house scripts to determine the functional parameters; blood-flow, surface permeability, plasma volume fraction and barrier transport constant. From the complex image the arterial input function (AIF) will be extracted in the major feeding arteries using the work by Simonis et al. (34). Baseline T1 measurements derived from the prescans will be used to convert the signal measured in dynamic scan into contrast agent concentration. The measured AIF will be used in the convolution of the monoexponential impulse response function minimizing the difference to the measured tissue concentration curves, thus allowing the extraction of haemodynamic parameters (35,36).

### **DWI**

The diffusion weighted imaging data will be used to calculate ADC maps (37). This sequence will acquire a set of different diffusion sensitive gradients (b-values). Excluding low b-values ( $<100-200 \text{ s/mm}^2$ ) the signal at higher b-values will be fitted using a monoexponential decay to extract the relevant diffusion coefficient (38). At higher field strength ( $\approx 3\text{T}$ ) local frequency shifts due an inhomogeneous background magnetic field ( $B_0$ ) may be observed. This will be corrected by an initial measurement of the  $B_0$ -field (39).

### **T1 quantitative**

The longitudinal relaxation rate is integral part of the DCE-MRI analysis and may be determined using a set of SPOiled Gradient Recalled echo (SPGR) sequences with varying nutation angles. This technique is known as the Variable Flip Angle (VFA) approach. By distributing the flip angles around the Ernst angle a reliable estimation of the longitudinal relaxation time may be performed.

### **T2 quantitative**

The transverse relaxation may be estimated using a set of T2-weighted sequences with different echo-times (TE). The decay in signal with increasing TE may be approximated to a single exponential with the characteristic decay constant being the transversal relaxation

rate. Compressed sensing techniques such as k-T SPARSE may be used to accelerate the data acquisition.

### **Machine Learning.**

For cervix tissue classification we will explore machine learning techniques like support vector machines (SVM), artificial neural networks (ANN) and convolutional neural networks (CNN)(40,41). We will combine both supervised and un-supervised classification techniques. An important step in both methods will be to eliminate the parameters that are not useful in distinguishing healthy and tumorous tissue (“feature selection”), since redundant parameters then can be avoided in future prospective designs. The output classification will be a set of probabilistic maps that will reflect the likelihood of tumour presence.

For the outcome measure training the use of SVM’s will likely be the most successful approach (16,42). The result will in this case be a probability of disease free survival for an unseen case. The validation of this training will be performed using a leave-one-out cross validation.

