## 3. STUDY DESIGN

This is an observational prospective, non-randomized study in which patients with locally advanced cervical cancer included in the EMBRACE II study can enrol. The study will be carried out in 8-15 EMBRACE centres.

MRI will be carried out prior to radiotherapy. The details of the MRI exams will differ from standard clinical practice in the centres, but will be consistent with international guidelines for cervix MRI. The exam will include T1, T2, diffusion, and dynamic contrast-enhanced imaging. At time of brachytherapy, the treatment planning MRI will additionally include DWI and qT2. Patients will be followed up according to the EMBRACE II follow-up schedule.

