#### 8.1.2 Secondary study parameters

Potential bias between centres will be evaluated for quantitative T2, quantitative DWI and DCE MRI parameters using ANOVA analysis. For DWI: the ADC (median tumour values) will be evaluated for assessment of any centre-effect.

We will investigate the use of machine learning techniques such as radiomics and deep learning in computer aided detection (CAD) of the primary lesion. The features used for this task will comprise of the full set and subsets of the functional and textural parameters extracted from DWI, DCE and qT2. The accuracy of the learned algorithm will be evaluated on a separate validation set with expert delineated primary lesion or a leave-one-out-cross validation.

Furthermore the DWI and qT2 will be tested whether they may predict disease free survival separately. The combination of all extracted functional (DCE, DWI, qT2) and textural features will be used to train a machine learning algorithm separating the classes: patients with and without disease free survival.

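### The outcome classifier uses a yes/no disease-free-survival class with no time point or handling of censoring, and its only validation, leave-one-out on pooled centres, cannot show performance in a new centre

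*Protocol*

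**What the plan says.** Section 8.1.2 combines the functional features (DCE, DWI, qT2) with textural features to "train a machine learning algorithm separating the classes: patients with and without disease free survival". Section 9 (Machine Learning) expects a support vector machine: "For the outcome measure training the use of SVM’s will likely be the most successful approach". On the output it says: "The result will in this case be a probability of disease free survival for an unseen case". On validation it says: "The validation of this training will be performed using a leave-one-out cross validation". No time point is attached to the class or to the probability.

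A separate validation set does appear in section 8.1.2, but for detection of the primary lesion, whose accuracy is to be "evaluated on a separate validation set with expert delineated primary lesion or a leave-one-out-cross validation". It is not offered for the outcome model.

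On the setting, section 3 states: "The study will be carried out in 8-15 EMBRACE centres". Section 8.2.1 states: "Participating centres will have different scanning platforms, with different vendors and different generation of scanners". The same section requires phantom scans and approval of each centre's sequences before that centre includes patients, and section 8.1.2 plans an ANOVA for centre effects. Neither is linked to the classifier or its validation.

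**The concern.** Section 4.4 treats disease-free survival as a time-to-event endpoint, with 3-year rates and a log-rank test. The classifier turns the same endpoint into two classes with no horizon. When patients enter over 4 years, their follow-up is unequal, and a class without a time point has no single meaning. A patient seen for six months without recurrence and one seen for five years could share a label. Some in the disease-free class would be failures not yet observed, so both training and reported accuracy would be distorted.

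The second issue is the unit left out. The text says only leave-one-out. The reference to an unseen case makes one patient at a time the natural reading. Each test patient's centre and scanner then remain in the training data. If features carry a scanner signature and event rates differ by centre, a model can gain apparent accuracy by recognising the centre. Whatever the size of that gain, the design cannot show how the model performs in a centre it has not seen.

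**Working it through.** **The plan's own figure.** Section 4.4 gives 3-year rates of 89% and 73% in equal groups, 80% power, 5% significance and 196 patients. The hazard ratio is ln(0.89)/ln(0.73) = 0.370. Freedman's formula, two-sided, gives 7.849 × (1.370/0.630)² = 37.2 events. The event probability is 1 − (0.89 + 0.73)/2 = 0.19, so N = 37.2/0.19 = 196. The figure reproduces, so the point rests on no sample-size error. The protocol gives no accuracy figure or sample size for the classifier.

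**Censoring.** Inputs from the protocol: 320 patients over 4 years (section 4.1) and average 3-year disease-free survival of 81% (section 4.4). Assumptions: uniform accrual, exponential times, no other loss to follow-up, a 3-year class, and every patient event-free at analysis labelled disease-free.

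- Hazard: λ = −ln(0.81)/3 = 0.0702 per year.
- Expected 3-year failures: 320 × 0.19 = 60.8.
- With analysis e years after the last accrual, follow-up is uniform from e to e + 4.
- Share event-free with under 3 years of follow-up: (1/4) × [exp(−λe) − 0.81]/λ.
- Share who would fail by 3 years but are still event-free: the previous share minus (1/4) × 0.81 × (3 − e).

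For e = 0 these are (1/4) × 0.19/0.0702 = 0.676 and 0.676 − 0.6075 = 0.069.

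| Years after last accrual | Event-free, under 3 years' follow-up (of 320) | 3-year failures labelled disease-free | Share of 60.8 |
|---|---|---|---|
| 0 | 216 | 22.0 | 36% |
| 1 | 139 | 9.5 | 16% |
| 2 | 67 | 2.3 | 4% |
| 3 | 0 | 0 | 0% |

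**Centre signature.** The documents give no figure for centre differences in features or outcome, so this part is a simulation under assumed effects: 8 centres of 40 patients, 50 pure-noise features, a 19% event rate, a linear ridge scorer standing in for the support vector machine, and 150 runs per setting. The feature shift between centres is in units of the within-centre SD.

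| Feature shift (SD) | Centre SD of log-odds of an event | AUC, leave-one-patient-out | AUC, leave-one-centre-out |
|---|---|---|---|
| 1 | 0 | 0.50 | 0.50 |
| 0.5 | 0.3 | 0.50 | 0.49 |
| 1 | 0.3 | 0.52 | 0.49 |
| 0.5 | 0.5 | 0.53 | 0.48 |
| 1 | 0.5 | 0.54 | 0.49 |
| 1 | 0.8 | 0.60 | 0.48 |

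The true AUC is 0.50 throughout. A second simulation, with 30 noise features, centre explaining 20-50% of feature variance and centre event rates varying by an SD of 8-10 points, gave 0.53-0.59 for leave-one-patient-out and 0.50-0.51 for leave-one-centre-out.

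Centre differences in outcome of that order could arise from case mix. Section 4.4 implies averages of (95 + 85)/2 = 90% in low-risk and (81 + 57)/2 = 69% in high-risk patients. Two centres with 30% and 70% high-risk patients (assumed) would differ by 0.4 × 21 = 8.4 points.

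**The case against.** The case against has several good parts.

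- **The labelling rule is not written.** A reader might infer that every patient event-free so far goes into the good class whatever the follow-up. The protocol does not say so, and a horizon or censoring rule may stand in an SAP that is not shown. This stands as a limit on the claim: mislabelling is possible, not established. What the protocol does fix is a two-class outcome and a probability with no time attached.
- **36% is the top of a range.** It needs analysis on the day accrual ends. The Summary's 4-year study duration equals the accrual period but is not a data cut, and section 8.2.5 leaves follow-up to the parent study. The sample-size formula takes 3-year event probabilities, which presumes 3 years of follow-up for all. On that premise the loss from staggered entry is zero. Even at the top of the range, 22/320, about 7% of labels, would be wrong.
- **Leakage is conditional.** It needs centres to differ in both features and outcome, and the simulated SDs are assumptions. A rise from 0.50 to 0.53 is less than one standard error of an AUC with 61 events and 259 non-events: √(321/(12 × 61 × 259)) = 0.04. The phantom procedure and the ANOVA are real safeguards. However, the phantom work compares quantitative values while the classifier also uses textural features, the GTV is drawn by each treating institution (section 9), and the ANOVA has no stated consequence for the model.
- **The multicentre objective does not ask for transport.** A reader might take it to require that the model work in a new centre. Section 2 asks about implementation of quantitative imaging, so that reading is not supported.
- **Leave-one-out is a recognised internal validation** and fits a prediction for an unseen case. That is a reason to add a second validation, not to discard the first.

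**Conclusion.** The point holds in a conditional form. The stated method sets a time-to-event endpoint as a yes/no class without a horizon, in conflict with how section 4.4 treats the same endpoint. It also validates the outcome model only by leave-one-out on pooled multi-vendor data. Early-censored patients can be mislabelled: from 36% of expected 3-year failures (22 of 61) with analysis at the end of accrual, down to none with 3 years of follow-up for all. Accuracy can be inflated by centre signatures: an AUC of about 0.53-0.60 from noise under moderate to large assumed centre effects, and little or nothing if outcome varies only slightly or not at all by centre. What needs no assumption is that leave-one-out on pooled centres cannot show performance in a new centre.

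A reader might infer that the planned accuracy is certainly biased, or that the main DCE-MRI result is affected. The documents support neither. The analysis is secondary, and the log-rank sizing of the main hypothesis is untouched.

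**What to change.** In sections 8.1.2 and 9, either use a time-to-event learner, or define the class as 3-year disease-free-survival status and apply inverse-probability-of-censoring weights. Attach the same time point to the predicted probability. Report leave-one-centre-out validation alongside leave-one-out, and repeat any outcome-driven feature selection and tuning inside each fold. The feature selection described in section 9 concerns healthy versus tumour tissue, so this last item is a precaution for the outcome model rather than a correction of stated text.

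The cost is wording and some computing; no new data are needed. The reported AUC will probably be lower and its interval wider. With weights, early analysis also has a price: at the end of accrual only about 320 − 216 = 104 patients would have known 3-year status, so a time-to-event learner would then use the data better.

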## **10. ETHICAL CONSIDERATIONS**

### **10.1 Regulation statement**

The collection of all data will be performed with written informed consent and according to national legislation concerning ethical requirements. Patient data will be stored and processed in the Department in accordance with applicable requirements. Transfer of anonymised patient data material between participating institutions will be performed with informed consent according to national and European law.

### **10.2 Recruitment and consent**

#### **Informed consent**

Specific patient information folders for the study will be produced. All patients will be informed of the purpose of the investigation, the possible side-effects, procedures and potential hazards to which she will be exposed.

Patients will be informed as to the strict confidentiality of their patient data, but that their medical records may be reviewed for study purposes by authorized individuals other than their treating physician.

It will be emphasized that the participation is voluntary and that the patient is allowed to refuse further participation in the protocol whenever she wants. This will not influence the patient’s subsequent care. Documented informed consent must be obtained for all patients

included in the study before they are registered at the Study Office. This must be done in accordance with the national and local regulatory requirements.

For European Union member states, the informed consent procedure must conform to the ICH guidelines on Good Clinical Practice. This implies that “the written informed consent form should be signed and personally dated by the patient or by the patient’s legally acceptable representative”.

Patients will be asked by the radiation oncologist about their interest in participating in the study. Written and oral information will be given by the doctor filling in the patient record and informing the patients about the forthcoming treatment.

**10.3 Objection by minors or incapacitated subjects (if applicable)**

Not applicable

**10.4 Benefits and risks assessment, group relatedness**

At present, the standard treatment for patients with locally advanced cervical cancer is EBRT, concurrent chemotherapy with Cisplatin and intracavitary BT. This treatment will also be used in the present protocol. The patients will be informed of the possible risks and side effects involved with the extra scan and contrast administration. If they do not wish to participate, this will not prevent them from obtaining the standard treatment. On this background it seems reasonable to conduct the investigation.

**10.5 Compensation for injury**

Health damage caused by trial participation is covered by the trial Insurance of the hospital, which is in accordance with the Legal requirements. The Insurance applies to the damage that becomes apparent during the study or within 4 years after the end of the study.

**10.6 Incentives**

Not applicable

## **11. ADMINISTRATIVE ASPECTS, MONITORING AND PUBLICATION**

### **11.1 Handling and storage of data and documents**

The investigators will ensure that this study is conducted in agreement with either the Declaration of Helsinki (Tokyo, Venice, Hong Kong, Somerset West and Edinburgh amendments) or the laws and regulations of the country, whichever provides the greatest protection of the patient. The patients will be anonymized. Clinical data will be entered in a web-based database where each enrolled patient is automatically assigned a sequential study patient ID number. The key between study ID number and patient identity is safeguarded in the enrolling institution according to local regulations for management of patient data. Imaging data will be anonymised and exchanged on a secure server.

The protocol has been written, and the study will be conducted according to the ICH Harmonized Tripartite Guideline for Good Clinical Practice. The protocol has been approved by the local Research Ethics Committee in accordance with national guidelines and legislation in the participating centres. The data will be kept 15 years.

### **11.2 Monitoring and Quality Assurance**

Not applicable

### **11.3 Amendments**

Amendments are changes made to the research after approval from local Research Ethics Committee. All substantial amendments will be notified to the local Research Ethics Committee. Non-substantial amendments will not be notified to the ethics committee, but will be recorded and filed by the sponsor.

### **11.4 Annual progress report**

Not applicable

### **11.5 End of study report**

Not applicable

### **11.6 Public disclosure and publication policy**

The results, regardless of positive or negative, will be published in the form of one or more articles in recognized international scientific journals in accordance to the Vancouver rules.

